Study 2: Our clinical study is a longitudinal randomized (6 month) cross over controlled clinical trial (RCT) intervention with two parallel arms (ratio: 1:1) with care-as-usual plus care coordination intervention. The purpose of Phase-II clinical trial is to examine effectiveness of the Care4AD platform to improve care coordination and caregivers burden and stress. For the purpose of this study, we will recruit 100 men and women older adults (Age 18+) persons with mild or moderate dementia/memory loss. Including self-reported memory loss and MOCA score of 26 or lower.

Both groups will receive identical Care4AD platform (tablet). However, all feedbacks (e.g., reminder about completed/incomplete tasks) will be activated in the intervention group (IG) and the caregiver will have companion app downloaded on their smartphone. Reminder notifications will be de-activated in the control group (CG) and no app will be supplied. CG will receive conventional care coordination intervention through bi-weekly interview and will be provided with

7/25/24, 1:58 PM Human Protocol Report
scheduled care tasks similar to IG. Participants will be informed that the purpose of this program is to examine effectiveness of a care coordination program to reduce stress and burden of care givers and improve adherence to scheduled care tasks and improve mobility. The type of intervention will not be disclosed to participants at baseline (blinded study design) as both groups will receive some sort of care coordination intervention. In addition, the person who will analyze the data will be blinded to the type of intervention. At the 3 month visit, participants will be crossed over to either intervention or control and follow procedures.

Inclusion Criteria:

Male and female older patients (> 18 years old) with mild or moderate memory loss, self- reported memory loss, or MOCA score 26 or lower, and who are ambulatory and are in a residential home with a caregiver/informant or in a nursing home.

Caregivers and Health Professionals will be included in the subject population.

Exclusion Criteria:

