At the baseline visit, we will perform the following measurements.

Medical History: We will record socio-demographics (e.g. age, gender, BMI, education, marital status, etc) and medical history (health status including comorbidities, history of falls, history of hospitalization, prior surgery, duration of diagnosed as MCI, co-existing medical conditions, hearing and visual performance, frailty status, etc), medication use, etc.

Questionnaires: We will ask the subject to answer a series of health related questionnaires such as quality of life (Promise Global), demographics, anxiety (Beck Anxiety Scale), instrumental daily living activities (Lawton-IADL), Pain-Mobility, fear of falling (FES-I), frailty (Fried Frailty), MOCA, MMSE or Trail Making A&B for cognitive status, and depression (GSD). Their caregivers will also be asked to complete the Zarit Burden Interview, a validated survey for dementia caregivers. These questionnaires will be completed through RedCap.

Phone calls: Research Coordinators will call subjects to ask health-related questions. They may also call the subject for study related questions.

Gait: Gait will be assessed using LEGSys, a validated body-worn sensor system. LEGSys uses five inertial measurement units attached to right and left anterior shins, right and left anterior thighs, and posteriorly to the lower back. LEGSys uses a two-link inverted pendulum model based on the subjects height to determine spatiotemporal gait parameters such as stride velocity, stride length, stride time, double support, single support, and stride-to-stride variability, and gait initiation. In addition, COM range of motion during walking will be calculated based on the data from the sensor attached to the lower back. Gait will be assessed under 2 conditions; walking at a habitual speed and walking at maximum speed. In addition,

Balance: Balance will be quantified using BalanSens, a validated body-worn sensor system. BalanSens measures ankle and hip motion in three dimensions, COM sway, and coordination between ankle and hip motion. Subjects will be asked to stand in different positions such as feet together and feet in semi-tandem with two conditions: eyes open and eyes closed.

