Spontaneous daily physical activity monitoring : Daily mobility performance and inactivity will be objectively monitored using a validated wearable technology named PAMSys, a sensor that can be worn as a pendant around the neck. We will assess multiple parameters such as number of taken steps, longest walking bout, standing duration, sedentary behavior, etc. Subjects will be monitored for up to 1 week continuously at baseline and at the end of the study. Subjects will be provided with a prepaid fedex envelop to return the Pamsys device to the research team.

Upper Extremity Test: Investigators will measure arm motion from each participant by implementing a validated technology based on wearable sensor system named LegSys. This system will assess respectively spatio-temporal parameters of arm motion as well as gait in a clinical setting. The LegSys system will be used with one sensor to capture arm motion, the sensor will be placed at the subject's wrist. While being at a comfortable position, the subject will be asked to flex and extend their arm for 20 seconds at a fast speed. Subject will also be asked to repeat this task but counting backwards as they flex and extend their arm (dual task).

Photos and media: We will be asking permission of the subject to take photos, film videos and/or record audio during the visits.

Care4AD: The research coordinator will provide the platform and explain to the subject and their caregiver how to interact with it. Together they will set up a schedule of regular IADL to follow. Intervention group will receive reminder notifications on their tablet to complete tasks and caregivers will be able to edit tasks on companion app downloaded on their smartphone. Control group will not receive reminder notifications and caregiver companion app will not be given.

Phone calls: Research Coordinators will call subjects bi-weekly to assess compliance to IADL schedule set up on the Care4AD platform. During the phone call, the coordinator will ask questions regarding acceptability and perceived usefulness and benefit of the platform. They may also call the subject for study related questions and to assess of there have been no adverse events (falls, hospitalization, etc).

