At the 3 month visit, the following procedures will be completed: Questionnaires, Gait, Balance, Motor-Cognitive Exercise program, Spontaneous physical activity monitoring, Upper Extremity Test, Photos and Media. Crossover will also happen, intervention group will become controls and controls will become part of the intervention group.

At 6 months, the following procedures will be completed: Questionnaires, Gait, Balance, Spontaneous physical activity monitoring, Upper Extremity Test, Photos and Media. At the end of the visit, the subject will return the platform to the research team.

Section G: Sample Size/Data Analysis

G1. Sample Size

How many subjects (or specimens, or charts) will be used in this study?

Local: 130 Worldwide: 130

Please indicate why you chose the sample size proposed:

Phase I: N=30 total subjects including 10 eligible Individuals With Dementia, at least one of the caregivers (n=10), and 10 expert clinicians unaffiliated with this project, who are providing care for Individuals With Dementia and their caregivers. The sample size for Phase I is chosen based on our experience with assessing technologies for older populations and also considering the timeline and budget limitation for Phase I. Over the past decade, we have evaluated the usability of a number of such technologies and we have found that the proposed sample size is adequate for identifying potential shortcomings that might require design or implementation modifications.

Phase II: N=100 total subjects, Individuals With care-givers, age 18+, who are supporting an individual with memory loss, aged 50+, male and female, who satisfied inclusion and exclusion criteria described in the following. The required sample size for Phase II was calculated based on our primary endpoints: 1) reduce burden for the caregivers in the Intervention group, 2) better adherence in the Intervention group compared to control group, and 3) change in functional performance over 6 month.

G2. Data Analysis

Provide a description of your plan for data analysis. State the types of comparisons you plan (e.g. comparison of means, comparison of proportions, regressions, analysis of variance). Which is the PRIMARY comparison/analysis? How will the analyses proposed relate to the primary purposes of your study?

7/25/24, 1:58 PM Human Protocol Report

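### Study 2 is labelled blinded, but patients and caregivers can see which features they have, so the caregiver-reported burden endpoint is effectively unblinded and at most the comparison is masked until crossover

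*Combined protocol and SAP*

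**What the plan says.** All references are to the combined protocol and SAP.

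- **Blinding claim (F1, Study 2).** "The type of intervention will not be disclosed to participants at baseline (blinded study design". The reason given is "as both groups will receive some sort of care coordination intervention". F1 adds that "the person who will analyze the data will be blinded to the type of intervention".
- **What the groups share (F1).** "Both groups will receive identical Care4AD platform (tablet". Controls also get a similar task schedule and bi-weekly contact.
- **What differs (F1, and F2 under Care4AD).** In the intervention group, reminders are active and "the caregiver will have companion app downloaded on their smartphone". F2 says: "Control group will not receive reminder notifications and caregiver companion app will not be given".
- **Crossover (F2, 3-month visit).** "intervention group will become controls and controls will become part of the intervention group".
- **Burden measure (F2, Questionnaires).** "Their caregivers will also be asked to complete the Zarit Burden Interview, a validated survey for dementia caregivers". The questionnaires are completed through RedCap.
- **Status of burden (G1).** Caregiver burden is the first of three listed primary endpoints, followed by adherence and functional performance.
- **Planned analysis (G2).** Linear mixed models for burden at 6 months against baseline and between groups.

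**The concern.** Not naming the arm at baseline differs from hiding it. The two conditions differ in exactly the things a user notices: whether the tablet prompts, and whether the caregiver has an app. The person who holds or lacks the app is also the person who scores the burden scale. F1 says participants are told that the programme aims to reduce caregiver stress and burden, so the direction of a favourable answer is known. The bi-weekly calls in F2 also ask how useful the platform seems.

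An expectation effect, if there is one, enters when the caregiver answers. A blinded analyst receives the score afterwards and cannot remove it. After month 3 respondents can compare the two conditions directly. If the label stands, a reader could take a burden difference to be protected from expectation when the design does not give that protection.

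**Working it through.** **1. Who is masked, to what, and until when**

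| Person | Months 0 to 3 | After the 3-month crossover |
|---|---|---|
| Patient | Sees reminders or sees none; may not know another version exists | Has met both conditions |
| Caregiver (completes the Zarit) | Has the app or does not; may not know another version exists | Has met both conditions |
| Coordinator | Provides and explains the platform (F2); masking not stated | Masking not stated |
| Staff doing gait, balance and cognitive tests | Masking not stated | Masking not stated |
| Data analyst | Blinded (F1) | Blinded (F1) |

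No sham app, sham notification, masked assessor or check of perceived allocation is described. The only masking of patients and caregivers that the text supports is of the comparison itself, and it ends at crossover.

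**2. The plan's own figure**

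The blinding claim has no figure attached. The Study 2 sample size of 100 (G1) cannot be re-derived, because no effect size, SD, power or dropout is given. The study total does add up: 30 + 100 = 130. For scale, 50 per arm (100 at 1:1, F1) detects (1.960 + 0.842) × √(2/50) = 2.802 × 0.2 = 0.56 SD with 80% power.

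**3. Illustration of what a reporting shift would do**

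Inputs: 50 per arm; significance level 0.05 (G2), taken as two-sided because the side is not stated; no true effect. The shift of b SD is assumed, since the documents give none. The comparison is between arms at 3 months, before crossover, by normal approximation.

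- Noncentrality: λ = b / √(2/50) = 5b
- Rejection probability: 1 − Φ(1.96 − λ) + Φ(−1.96 − λ)

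| Assumed b | λ | Rejection probability |
|---|---|---|
| 0 | 0 | 0.050 |
| 0.1 | 0.5 | 0.079 |
| 0.2 | 1.0 | 0.170 |
| 0.3 | 1.5 | 0.323 |

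G1 counts patients and caregivers separately for Phase I. If the 100 were counted that way too, there would be 50 pairs and 25 per arm. Then λ = b / √(2/25), and the last three rows become 0.064, 0.109 and 0.186. F1, which speaks of 100 patients, favours 50 per arm.

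**4. Limit of the illustration**

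G2 tests burden at 6 months. By then both sequences have had both conditions, so a constant shift between arms does not describe that contrast. These rates apply only to a 3-month parallel comparison.

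**The case against.** The strongest reply is that F1 claims little: non-disclosure at baseline, justified because both groups receive care coordination, plus a blinded analyst. With an identical tablet, similar tasks and regular contact, a control pair may believe it has the programme under study. That stands for the first three months, so a reader who infers that the trial is simply open-label throughout, with nobody masked to anything, goes further than the text allows.

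Four other strong readings are tempting and also unsupported.

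- **Only the analyst could be blinded.** Nothing prevents masked assessors for gait, balance and cognition. The documents are silent. Nor do they say who switches reminders on or off.
- **Platform-logged task completion is an objective check already available in both groups.** No section says that it is recorded for controls. F2 assesses compliance through coordinator calls, and F1 turns off feedback on completed and incomplete tasks for controls. If logging needs a user response, reminders could change the record itself.
- **Effectiveness rests on burden alone, or must be shown jointly with other outcomes.** G1 lists three primary endpoints. Requiring joint evidence is a debatable trade-off, not something this inconsistency demands.
- **The result will be reported as blinded.** No reporting plan says so.

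It is also fair that F1 classes the work as a pilot, that participants in behavioural technology trials often cannot be blinded, and that F2 lists questionnaires first and crossover last at 3 months. That list does not set an order. None of this rescues the label, because masking the hypothesis is not blinding to treatment.

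**Conclusion.** The concern holds in a limited form. F1 describes a property that Study 2 lacks for the caregiver-completed Zarit score. Patients and caregivers are effectively unblinded to the features they receive. Masking of the comparison may last until month 3 but not beyond, and analyst blinding does not protect the score.

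This follows from F1 and F2 without any assumed number. It takes the Zarit to be among the questionnaires repeated at 3 and 6 months. The rates of about 8%, 17% and 32% show what assumed shifts of 0.1, 0.2 and 0.3 SD would do. They are not evidence that burden scores are biased, and they say nothing about the size of any bias at 6 months. The fault is an overstated label and an unspecified order of steps, not the choice to run an unblinded behavioural trial.

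**What to change.** 1. In F1, replace the blinded label with: open-label to participants and caregivers, with non-disclosure of the comparison until crossover and a blinded data analyst. State whether the staff who run the gait, balance and cognitive tests are masked.
2. In F2, require caregivers to complete the Zarit in REDCap at the 3-month visit before any crossover step or explanation. How much this protects depends on what participants were told earlier about the switch. The consent pages are not in the reviewed text, so the sponsor should check. It does nothing for the 6-month score.
3. In G2, report burden as unblinded self-report, and treat the pre-crossover 3-month comparison as the one least affected by awareness of both conditions. Interpret it beside the sensor-measured gait, balance and activity collected in both groups. These are patient outcomes, so they give context and do not confirm a change in burden. For activity, settle the timing first: the monitoring paragraph in F2 names baseline and end of study, the 3-month list adds it, and neither says whether that week falls before the switch.
4. Do not rely on platform-logged task completion unless the sponsor confirms that it is recorded the same way with reminders off.

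The cost is protocol wording and visit order, with no added participants or devices. The drawback is that the stated design becomes slightly less favourable.

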Study 2: Results of the user experience questionnaires will be calculated as median (range) for each Likert-scale question. Unpaired t-tests, Mann-Whitney u-tests, and Chi-square will be used for baseline between groups comparison to verify effectiveness of randomization. Linear mixed models will be used to test the effect of the Care4AD care coordination intervention on caregiver burden/stress at 6 months compared to baseline and between groups. Mixed models that accommodate the longitudinal design, allow for testing differences between groups in patterns over time, as well as at specific time points are consistent with an intention to treat analysis, and are valid for data which are missing at random. Appropriate mixed models (linear for continuous or Generalized Estimating Equations (GEEs) for non-continuous or non-parametric variables) will be used to test the intervention effect for each of the secondary outcomes (depression, cognitive function, QoL, fear of falls, neurotic tendency including fatigue, physical activity, adverse events, missing appointments). Univariate linear regression analyses will be performed to delineate predictive factors of training response for the primary study endpoint (pre- to post- changes in care coordination outcomes). Baseline values include age, gender, BMI, fear of falling, ADL-status, comorbidity, cognitive performance, depression, stage of AD, and baseline motor variables (e.g., balance and gait speed). We will use Spearman correlation coefficient to compare changes in quantitative metrics of exercise performance over the course of the program with in clinic assessments of functional performance (e.g., gait speed) and cognitive performance (e.g., MoCA). We will assess the agreement between Care4AD derived ADL, the Katz Index, and the Lawton-ADL. To demonstrate the acceptability of Care4AD application, we will use TAM model described above using 5-point Likert response questions. For all assessments, a p-value of 0.050 or less will be considered as statistically significant level. To evaluate the effect of sex as biological variable, we will examine whether acceptability and benefits of Care4AD platform to improve care coordination outcomes (between groups as well as compared to baseline) are different between men and women.

Section H: Potential Risks/Discomforts

H1. Potential Risks/Discomforts

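### Adherence is a primary endpoint, but its only described source is a bi-weekly call to subjects with memory loss by staff not stated to be masked

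*Combined protocol and SAP*

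**What the plan says.** **Status of the endpoint.** G1 says the Phase II sample size was based on three primary endpoints. The second is "better adherence in the Intervention group compared to control group".

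**How adherence is collected.** Under Study 2 phone calls, F2 says: "Research Coordinators will call subjects bi-weekly to assess compliance to IADL schedule set up on the Care4AD platform". The same call covers acceptability and the perceived usefulness and benefit of the platform, and may cover adverse events. The lists of procedures at baseline, 3 months and 6 months contain no other adherence measure. G2 defines no adherence variable, time window, scoring rule, data source or model.

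**Who is asked.** F1 describes the Study 2 sample as "persons with mild or moderate dementia/memory loss. Including self-reported memory loss and MOCA score of 26 or lower". F1 also says: "Caregivers and Health Professionals will be included in the subject population".

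**Who asks.** Coordinators also deliver the platform: "The research coordinator will provide the platform and explain to the subject and their caregiver how to interact with it". F1 states masking for participants at baseline (the type of intervention is not disclosed) and for the data analyst. It mentions no masked caller.

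**What the platform does.** Both groups receive the same tablet platform. Control has reminders switched off and no caregiver app (F1, F2). Section C describes the platform as monitoring activities of daily living, and F1 describes feedback on which tasks are done or not done. In G2, platform data appear only here: "We will assess the agreement between Care4AD derived ADL, the Katz Index, and the Lawton-ADL".

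**The concern.** The call is the stated route to a primary endpoint, and three features make it fragile.

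- The respondent is, on the plainest reading of F2, a person with memory loss who is asked by telephone at two-week intervals. The section describes no log or informant to support the answer.
- The condition is visible. One arm has reminders and a caregiver app and the other does not, and the caller belongs to the staff group that hands over the platform.
- Asking about adherence and about the platform's benefit in one conversation lets opinion of the platform colour the adherence answer.

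Reminders could lead people to report more completed tasks, or make them more aware of missed ones. Either way the reported difference would mix behaviour with reporting, and the test could not separate them. There is also a possible overlap with the comparator: F1 delivers the control group's care coordination by bi-weekly interview, and the documents do not say whether that is the same contact as the adherence call.

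**Working it through.** **Can N=100 be reproduced?** No. The documents give no effect size, SD, power or dropout. Assuming a two-sided 0.05 test with 50 per arm in parallel, the detectable difference at 80% power is (1.96 + 0.84) × √(2/50) = 0.56 SD. That is a back-calculation, and nothing in the plan contradicts it.

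**Effect of reporting that differs by condition, with no true effect.**

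Inputs from the documents: 100 participants, 1:1 allocation, crossover at 3 months, significance level 0.05. Assumed: two-sided test, normal approximation, no dropout, bias b in SD units, within-person correlation ρ.

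Formula: false-positive rate = Φ(b/SE − 1.96) + Φ(−b/SE − 1.96).

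- Parallel, 50 v 50: SE = √(2/50) = 0.20.
- Crossover, 100 participants, ρ = 0.5: SE = √(2(1 − 0.5)/100) = 0.10.

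| Bias b (SD) | b/SE, parallel | False-positive rate, parallel | b/SE, crossover | False-positive rate, crossover |
|---|---|---|---|---|
| 0.1 | 0.5 | 7.9% | 1.0 | 17.0% |
| 0.2 | 1.0 | 17.0% | 2.0 | 51.6% |
| 0.3 | 1.5 | 32.3% | 3.0 | 85.1% |

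With ρ = 0.3 the crossover rates are 13.5%, 39.4% and 71.8%. With ρ = 0.7 they are 25.2%, 73.3% and 97.2%.

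**Why the crossover does not help.** In a within-person comparison, each person's own habit of over- or under-reporting cancels. A bias attached to having reminders on does not cancel, because it is present in the reminder period and absent in the other period for everyone. The crossover shrinks the standard error and leaves the bias untouched, so the same bias produces more false positives.

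**The case against.** Four objections carry weight.

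1. **The respondent is ambiguous.** F1 counts caregivers among the subjects, and G1 describes the Phase II subjects in words that read as caregivers. F2, however, names the subject and the caregiver separately, so the patient is the natural reading. If caregivers do answer, those in the reminder condition hold an app and the others do not, so reports can still differ.

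2. **Some steps are inferences.** The documents do not use the word recall. They do not say that the person who sets up a tablet makes the calls to that household, or that callers know the condition. They also do not say that the call is the sole source. It is the only one described.

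3. **Platform measurement may already be intended.** A reader might infer that the sponsor holds a completion log for both conditions and has chosen recall over it. The text does not support that. Feedback on done and undone tasks is described only as active in the intervention group, and nothing says that logging continues when feedback is off. It is also unclear whether completion is sensed or entered by hand. A hand-entered log prompted by reminders, or edited through the caregiver app, could itself differ by condition, so making the log primary for every task would be unsafe.

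4. **Recall error that is equal in both conditions costs less power than it may seem.** A reader might infer that misreporting with sensitivity and specificity of 0.8 shrinks the difference to 0.6 of its size and so halves power. That would require the SD to stay fixed. For a per-person proportion p, the reported value is 0.2 + 0.6p, so the between-person SD shrinks by 0.6 as well. Take an unfavourable assumed case: mean 60%, between-person SD 0.15, 70 tasks, true difference 0.56 × 0.15 = 0.084.
   - True completion: variance 0.0225 + (0.24 − 0.0225)/70 = 0.0256, effect 0.084/0.160 = 0.525 SD, power Φ(0.525/0.20 − 1.96) = 75%.
   - Reported completion: variance 0.0081 + (0.2464 − 0.0081)/70 = 0.0115, effect 0.0504/0.107 = 0.470 SD, power 65%.

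   With 200 tasks or a larger between-person SD the loss is smaller. Dilution is a minor issue, and differential reporting is the main one.

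**Conclusion.** The concern holds in this form: a primary endpoint rests, as described, on a bi-weekly call to subjects with memory loss, made by staff outside the stated masking, in a conversation that also asks about the platform's benefit. Reports can differ by condition, and neither the crossover nor the masked analyst corrects that.

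The size is illustrative. The error rates of about 8 to 32% (parallel) and 17 to 85% (crossover, ρ = 0.5) follow from an assumed bias of 0.1 to 0.3 SD. The documents give no basis for the true value or its direction. They do not show that such a bias will occur, only that the described procedure does not guard against it. No figure in the plan is contradicted.

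The protocol should be changed before adherence is analysed as a primary endpoint. The better method would draw on devices and caregivers already in the trial, subject to confirming what the platform records in control periods.

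**What to change.** 1. In G1 and G2, define the primary adherence endpoint as the proportion of scheduled tasks completed in each 3-month period.
2. State which tasks the platform captures automatically and identically in both conditions. For these, keep capture running in the background when feedback is off, and use that log as the primary source.
3. For all other tasks, including any marked complete by hand, use the caregiver's report, taken by one fixed script in both conditions. Ask the platform-opinion questions after the adherence items.
4. Keep the subject's bi-weekly self-report as a secondary source.
5. State who answers the call, whether the caller knows the current condition, and whether this call is the same contact as the control group's bi-weekly interview.

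The cost is a protocol edit, a data export and a check that control-period logging works. Some tasks will still rest on report, and a caregiver who has the app may report differently from one who does not. Results should therefore be shown separately for logged and reported tasks.
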